Study Protocol

Study Name: Genomic and Imaging Study for Patients Undergoing Surgery for Liver Cancer

Principal Investigator: [name] [name]

Primary study site: The Queen's Medical Center, Honolulu, Hawaii

Primary site identifier: RA-2011-025

NCI CTRP identifier: NCI-2012-02095

Clinicaltrials.gov identifier: NCT01395030

IRB Approved Version Date: August 18, 2014

Next IRB approval expiration date: September 30, 2018

Study Name: Genomic and Imaging Study for Patients Undergoing Surgery for Liver Cancer

Principal Investigators: [name]

Detailed Study Protocol

I.1. Study Protocol Schedule

Enrollment:

- Signed consent form and completed eligibility checklist (Oncology Research Department (ORD) Nurses to complete Patient Selection Criteria and Enrollment).
- Relevant clinical documentation is reviewed by the PI ([name]) prior to authorization to schedule PET/CT appointment.
- Serum pregnancy test is performed (if appropriate).
- PET/CT appointment is scheduled.

Imaging Appointment (1.5h):

- PET/CT using Liver F-choline Scan Protocol within 14 days of surgery.

Day of Surgery:

- UHCC Pathology Shared Resource personnel are notified and available for specimen procurement.
- Specimen obtained under UHCC Specimen Procurement Standard Operating Procedure (see Appendix following this Protocol).

Follow-up

- Blood tests which include a comprehensive metabolic panel (includes liver function and chemistry panel), protime and complete blood count will be drawn at the subject's 1-4 week follow-up visit with their surgeon. These tests will be performed by a certified diagnostic laboratory such as DLS. If subject agrees, an optional research blood sample will also be collected and sent to UHCC for analysis.
- Subjects are also enrolled into the Hawaii Tumor Registry. Therefore, the ORD staff will not be involved in extended follow-up data collection, given that this falls within the scope the State-mandated tumor registry activities.

I.2. Criteria for Patient Selection

Inclusion Criteria: **Inclusion Criteria:** 1) > 18 years of age. No upper limit of age. 2) liver tumor diagnosed histologically as HCC or suspected of being HCC in association with serum alpha-fetoprotein level > 200 or tumor mass with characteristics of malignancy on diagnostic imaging, 3) under the care of a surgical attending, 4) deemed a surgical candidate and has agreed to surgery to remove a portion of the liver containing tumor, and 5) Child-Pugh A/B.

Exclusion Criteria: 1) Weight > 350 lbs (PET/CT limit); 2) pregnant or lactating female, a serum pregnancy test will be performed within 2 weeks or less before the date of the FCH PET/CT scan in all women capable of becoming pregnant; 3) serious underlying medical condition that would impair patient's ability to tolerate the imaging procedure; 4) concurrent treatment with chemotherapy, molecule-selective, biological, or radiotherapeutic agent.

I.4. Method of Enrollment and Follow-up

Written informed consent will be obtained by the PI or other physician listed on FDA Form 1572. The Research Nurse ([name] or other ORD nurse) or Associate ([name] or other ORD Associate) will assist the PI with recruitment, enrollment, scheduling, and follow-up.

If the subject experiences a serious adverse event, follow-up of the adverse event to its conclusion will ultimately be the responsibility of the PI and the IND sponsor-investigator (who serves as co-investigator on this study). The patient's treating physician will be allowed to assist with clinical follow-up.

I.4.1. Authenticating Disease Progression

Clinical information (test results, etc.) will be reviewed for the purpose of confirming inclusion/exclusion criteria.

Evidence of disease progression will be collected and made available for descriptive purposes and retrospective analyses. Data collection to support authentication of disease progression will include documentation of patient demographics, age, performance status, clinical stage, details and dates of the primary therapy, and post-treatment clinical status. The presence of potential disease sites will be documented based on reports of any available imaging studies including but not limited to CT, MRI, ultrasound, and bone scan. This data will be assembled on study specific forms by the personnel for this study. The PET image data and genomics data are high-dimensional datasets. This type of data will not be available in study forms but will remain in their source format. The survival data will also not be collected by study personnel or entered into the study specific forms, since they will be obtained directly from the Hawaii Tumor Registry through query reports.

I.5. Method for Determining Doses, Maximum dosage, and Duration of Patient Drug Exposure

Patient dose has been determined by the least radiation dose from the radiopharmaceutical that will provide enough counts in the tomograph detectors to obtain quantifiable images with adequate counting statistics. The exposure of the patient to the radiopharmaceutical will only be until the radioactive label decays. The half life of fluorine-18 is 109.8 minutes. Maximum duration of radiation exposure is therefore limited by this half-life. The number of doses administered is determined by the number of PET/CT scans required by the study protocol. The total effective dose will not exceed reasonably safe limits set by the FDA as described in the investigator's brochure for 18F-choline. Each dose of 18F-choline is administered intravenously as a single unit dose. A radioactivity dose of 0.09 millicuries per kilogram of body weight will be prescribed and obtained from the cyclotron laboratory. A dose calibrator in the PET imaging suite will be used to confirm the actual dose to be administered. Only a dose falling within a 10% range of the calculated prescribed dose will be administered.

I.6. Observations and Measurements to Fulfill the Objectives of the Study

Source documents (clinical, radiographic, and pathology reports), obtained from the medical record (office or hospital) following subject written informed consent, will be abstracted to generate a list of known sites of active disease. A table of these sites for each subject will be entered into a password-protected database.

I.7 Investigational Observations and Measurements to Fulfill the Objectives of the Study

The 18F- Choline injection is infused into the subject intravenously over 1 minute. The PET scanning is started approximately 10 minutes after the start of infusion. PET imaging data, from the neck to the proximal femur is then collected. PET data is analyzed by: a) visual assessment, and b) semi-quantitative region of interest (ROI) analysis. Standardized uptake values (SUV) will be recorded from each ROI. Implicit in the definition of SUV is the requirement that the tomograph be properly calibrated so that activity in tissue can be determined in uCi/ml. Structural imaging (CT, MRI) when available will be used for anatomical correlation. If a PET/CT scan is performed, the CT performed for attenuation correction will provide some anatomical correlation data. The PET/CT imaging protocol is described in section I.10.

Patients will routinely schedule follow-up visits with their surgeons at 1-4 weeks post-op. After this visit, the

study will perform blood tests which include a complete blood count, protime and comprehensive metabolic panel (CMP). These tests will be provided through a commercial testing laboratory (eg. Diagnostic Laboratory Services, Inc.). The results of these clinical laboratory test results will be compared to the pre-operative PET imaging findings to investigate whether PET may be predictive of post-surgery liver function. This is consistent with Specific Aim 3 of the research study.

If the research subject agrees, additional research blood samples will be obtained immediately before and 1-4 week following liver resection surgery. These samples will be sent to UHCC for analysis. If the patient is having other blood tests, these samples can be collected with the other tests. Using sterile technique, an intravenous needle will be inserted by a trained IV technician into an arm vein. A total of approximately 4 tsp of blood will be withdrawn into two vacutainer tubes. The sample centrifuged to isolate plasma fraction, buffy coat, and pellet. These samples will be frozen and analyzed in batches later to provide data on germline DNA, RNA, microRNA, and circulating RNA/DNA. The same procedure will be applied to the pre-surgery and post-surgery sample collections. If the results of a recent (within 3 months) fasting lipid profile (ie. cholesterol blood test) are not available, a fasting lipid profile will be obtained by Diagnostic Laboratory Services at the time other baseline laboratory samples are being obtained by the study. This information will be compared with the PET imaging and tissue expression data, providing reference values for the genomic analyses (Specific Aim 2). These blood samples will be used only to pursue the goals of this study, and will not be stored and made available to other research studies.

I.8. Clinical Procedures or other Measures to Monitor the Effects of the Drug in Human Subjects

Vital signs (e.g., temperature, heart rate, blood pressure, respiratory rate) will be measured on each subject prior to radiotracer administration. Vital signs will be repeated at the conclusion of PET imaging. During and after the PET/CT scanning procedure, subjects will be asked if they are experiencing any unusual symptoms.

I.9. Policy regarding human subjects and informed consent

Research involving human subjects is covered by federal law and institutional policies. All research conducted at our institution requires review and pre-approval by a Scientific Review Committee followed by approval from an Institutional Review Board. Subjects will be given a Queen's Medical Center IRB-approved consent.

I.10. PET/CT Protocol

Instrument: Gemini TF-64 PET/CT (Philips Medical Systems N.A., Bothell, WA)

Scan Protocol: Low-Dose CT, Liver PET Protocol

Isotope Dose: 18F-Fluoromethylcholine, **0.09 mCi/kg** patient body weight on day of scan.

1. A copy of the signed consent form will be faxed to the Research Regulatory Office.
 2. Height, sex, and age of the patient are recorded. Body weight, blood pressure, pulse, temperature and respiratory rate are obtained. The obtained weight is used to determine 18F-choline dose.
 3. Using sterile technique, an intravenous catheter is inserted by a trained IV technician into an arm vein. The catheters are flushed with sterile saline. The patient is placed in the supine position on the scanning table.
 4. A vial of 18F-choline containing a dose of 0.09 mCi/kg of body weight will be obtained from the cyclotron laboratory. A dose calibrator in the PET imaging suite will be used to confirm the actual administration dose. Only a dose falling within a 10% range of the calculated prescribed dose will be administered.
 5. A topographic scan will be performed to identify anatomical boundaries and the axial imaging field of view. The field of view is to encompass the liver, with 1cm margin from the upper limit of the field.
 6. A CT transmission scan in the supine position is acquired over the upper abdomen. The 64-channel helical CT scanning parameters were: 120 kV, 30-50 mA/slice, rotation time 0.75 sec, slice thickness/interval 5.0mm. No intravenous contrast will be used with CT.
 7. The 18F-choline is injected by bolus followed by a 10 cc saline flush. Image acquisition is begun immedi-
-

ately with the flush in a dynamic mode using the following timing schema:

Frame #	Duration (seconds)
1-20	10
21-23	40
24-27	120
28-30	240
31	360

However, if it is determined in the initial 5 subjects that the dynamic imaging data fits well into a 1-tissue kinetic model of FCH uptake where activity levels eventually plateau or become linear, then the dynamic scan can be shortened (to 12-15 minutes, for example) and the dynamic frames curtailed accordingly.

8. A short 3-minute static scan of the liver will be performed subsequent to the dynamic scan, and rapidly reconstructed to provide the investigators an immediate image for review of quality control and biodistribution. The operating characteristics of this PET device are described elsewhere (Surti S, et al. *J Nucl Med.* 2007;48(3):471-480.)
9. After the scan, patient blood pressure, pulse, respiratory rate, and temperature are measured and recorded. Subjects are released pending investigator review of the vital signs and flow sheet.
10. Image reconstruction will employ a list-mode version of a maximum likelihood expectation maximization algorithm with a time-of-flight kernel applied in both the forward- and back-projection operations. CT data is used for attenuation correction. Reconstructed images in 3 orthogonal planes will be reviewed on a dedicated PET/CT viewing station and will be archived on removable media in DICOM format.

I.11. Facilities Data

The facilities used to carry out the activities described in this document are located at the Queen's Medical Center, [name]. These facilities include the Hamamatsu/Queen's PET Imaging Center which houses the tomograph, and the Liholiho Cyclotron Building which houses the accelerator. The accelerator used to produce radioisotopes is an 11 MeV RDS-111 (CTI, Knoxville, TN) with the required beam line and targetry systems. The radiochemistry laboratories house production systems and robotics, a pneumatic system for transfer of radiopharmaceutical to the imaging area, and adequate equipment and laboratory space for radiopharmaceutical production and quality control. The hot lab contains 2 hot cells (Von Gahlen, Netherlands), organic chemistry space for compound production and development, and a small radiopharmacy in the imaging suite. There is 110 square feet of radioanalytical instrumentation and desk space for radiochemistry work.

Handling of all radioisotopes is conducted under the supervision of the hospital Radiation Safety Office (RSO). RSO personnel will regularly monitor the radiopharmaceutical laboratories for radioisotope contamination. All personnel using radioisotopes will wear a film badge and those handling isotopes will wear finger ring badges to monitor integrated radiation absorbed dose. Disposal of radioactive waste is only in specially designated and properly shielded receptacles. The laboratory is monitored for radioactivity by external monitoring and wipe tests. The short half-life of fluorine-18 insures that no long-term radiation safety problem is engendered. All equipment is tested regularly as to its operation. Specifically, the dose calibrator is tested for constancy each day it is used, its linearity quarterly, and its accuracy annually. Logbooks record these measurements. Radiation survey instruments, including safety monitors (hand and foot) and personal dosimeters, are calibrated at least annually and following any repairs. All calibration procedures and schedules for radiation monitoring devices are reviewed and approved by the RSO. The PET imaging facilities are located in the first floor of Queen's Medical Center, adjacent to the Nuclear Medicine clinic. This area houses the PET/CT device. There are existing waiting rooms and patient examination facilities in the clinic and physician and nursing personnel are available on premises. The rooms of the PET suite are the 1) two tomograph rooms, one containing a Hamamatsu SHR-22000 PET system, and another containing a Philips Gemini TF PET/CT scanner with 64-slice CT, 2) a control room with a small radiopharmacy laboratory, 3) the administration and patient holding room, and the 4) a data analysis and display room located in the Nuclear Medicine clinic.

I.12. Institutional Review Board Data

This study with [¹⁸F] fluorocholeline requires review by the Queen's Medical Center Institutional Review Board. Our institutional review process is composed of two parts. A Scientific Review Committee (SRC) preliminarily reviews all new research proposals with the exception of retrospective studies. If passed by the SRC, an Institutional Review Board (IRB) will then conduct the initial and continuing review and approval of any project involving human subject research. The address of the Queen's Medical Center IRB is:

Research and Institutional Review Committee
Institutional Review Board
The Queen's Medical Center

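### Does the split of follow-up between study staff and the tumor registry leave disease progression without a collector or an end date?

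*Protocol*

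**What the plan says.** Four sections of the protocol bear on this.

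- **I.4.1 (Authenticating Disease Progression)** states the purpose: "Evidence of disease progression will be collected and made available for descriptive purposes and retrospective analyses". The items listed are mainly baseline characteristics, together with details and dates of the primary therapy and the clinical status after treatment. Potential disease sites are documented "based on reports of any available imaging studies including but not limited to CT, MRI, ultrasound, and bone scan". On who does the work: "This data will be assembled on study specific forms by the personnel for this study". Survival is set apart: "The survival data will also not be collected by study personnel or entered into the study specific forms", because it comes from Hawaii Tumor Registry queries.
- **I.1 (Follow-up)** schedules blood tests at the surgeon's visit 1-4 weeks after the operation. It then says that "the ORD staff will not be involved in extended follow-up data collection", "given that this falls within the scope the State-mandated tumor registry activities".
- **I.4** says that the research nurse or associate, both ORD roles, "will assist the PI with recruitment, enrollment, scheduling, and follow-up".
- **I.6** provides that clinical, radiographic and pathology reports from the office or hospital record "will be abstracted to generate a list of known sites of active disease".

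The protocol shown gives no surveillance imaging schedule, no definition of progression and no date up to which progression is to be abstracted.

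**The concern.** Read in sequence, the sections seem to leave a hole. I.1 hands extended follow-up to the registry, but I.4.1 takes only survival from it, and no section says that the registry supplies progression. Progression therefore stays with the study. Yet the only staff named as helping the principal investigator with follow-up are the ones that I.1 withdraws, and the last scheduled contact comes within a month of surgery, too early to show most progression after a resection.

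If that reading were right, later progression would be known only for subjects who happened to be scanned in routine care and whose chart someone opened. A subject with no recorded progression could be progression-free or simply not examined. If the date of last imaging were never captured, no later analysis could tell the two apart, and a comparison of progression with PET or genomic findings could reflect who was scanned.

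**Working it through.** The protocol states no sample size, event count or progression rate on this point, so there is no figure of its own to reproduce. The check sets the sections side by side.

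**1. Is the task assigned?** Yes. I.4.1 gives it to study personnel in general. The assignment names no role, but it exists.

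**2. Does I.1 cancel that assignment?** Not fully. I.1 excludes the ORD staff and nobody else. I.4 also mentions the principal investigator, the other physicians listed on the FDA form, and a co-investigator who holds the IND. Any of them can abstract a chart without breaching I.1.

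**3. Do I.1 and I.4 contradict each other on ORD follow-up?** Not necessarily. I.4 assigns ORD help with follow-up and gives no duration. I.1 excludes *extended* follow-up and gives registry coverage as the reason. ORD help up to the 1-4 week visit, and none for registry-type follow-up after it, satisfies both.

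**4. Does recording depend entirely on imaging?** No. I.4.1 lists clinical status after treatment as an item of its own, and it needs no scan. The sentence on available imaging concerns potential disease sites and has no time frame. Since I.4.1 opens with confirmation of eligibility and most of its listed items are baseline ones, that sentence may describe baseline sites, much as I.6 does.

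**5. Would the information be lost?** Probably not. I.6 already provides for abstraction of reports from the medical record after consent. If those reports are dated and kept (an assumption, though an ordinary one), the date of last imaging can be read from the chart later. I.4.1 itself plans retrospective analyses.

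**6. How large could the effect be?** Let p be the proportion progressing among subjects with information and u the share with none. If nothing is assumed about the latter, the cohort proportion lies between

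- lower = p(1 − u), where none of them progressed;
- upper = p(1 − u) + u, where all of them did.

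With p = 0.30 (assumed):

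| u (assumed) | lower | upper | width |
|---|---|---|---|
| 0.10 | 0.30 × 0.90 = 0.27 | 0.27 + 0.10 = 0.37 | 0.10 |
| 0.20 | 0.30 × 0.80 = 0.24 | 0.24 + 0.20 = 0.44 | 0.20 |
| 0.40 | 0.30 × 0.60 = 0.18 | 0.18 + 0.40 = 0.58 | 0.40 |

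The arithmetic is right, but the width is u whatever p is. That holds for any yes/no variable with missing values, so it does not show that u is large in this trial. The protocol gives neither p nor u. The bounds also treat a subject without imaging as wholly uninformative, which step 4 contradicts.

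**The case for a change.** The strongest reply is that responsibility for collecting data is protocol content. An analysis plan can fix a cut-off date and a censoring rule, but it cannot recover an item that nobody was told to collect. A generic assignment with no end date binds no one in practice, the more so when the staff who would normally do the work are excluded. Aligning the sections would take a few words and one chart review per subject, with no added visits or scans.

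Part of this stands. The protocol shown names no specific role after the 1-4 week visit and gives no end date for abstraction, and I.1, I.4 and I.4.1 would read better if aligned. Uneven ascertainment is possible.

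The rest goes further than the text. Uneven recording is something that *could* happen; no stated rule makes it happen. The claim of irrecoverable loss also sits badly with the proposed cure: one later chart review per subject works only if the dated reports are still in the record, and in that case little has been lost. Censoring at last imaging presupposes a time-to-event analysis of progression that the protocol does not promise. The coding of subjects without imaging and the common cut-off are details that an analysis plan or the study forms commonly carry. Those documents are not shown, so their absence here is not evidence of a gap.

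**Conclusion.** No change to the plan follows. This is a loosely worded division of work that the investigators can fill sensibly, and no rule in the protocol gives a wrong result. The task is assigned, the exclusion in I.1 is confined to one group of staff, survival has a defined source, and the chart route in I.6 remains open.

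What is exposed is limited. The protocol shown attaches no endpoint or test to progression, and its use is descriptive and retrospective. The comparison of PET findings with liver function after surgery (Specific Aim 3, described in I.7) rests on blood tests from the 1-4 week visit and is unaffected. The size of any unevenness cannot be derived from the protocol, and the ranges above only illustrate assumed inputs.

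The conclusion rests on three conditions: dated imaging and clinical reports stay retrievable from the medical record; the forms or analysis plan, which are not shown, set a common cut-off and separate absence of progression from absence of information; and progression keeps its descriptive role. The Specific Aims are mentioned but not set out in the text shown. If one of them made progression an outcome for inference, the role and the observation window would matter more.

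### Aim 3 sets post-operative liver tests against pre-operative PET without stating that the same tests are recorded before surgery; adding them is a cheap improvement

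*Protocol*

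**What the plan says.** Section I.7 sets out the Aim 3 comparison: post-operative results of the complete blood count, protime and CMP are to be "compared to the pre-operative PET imaging findings to investigate whether PET may be predictive of post-surgery liver function".

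The schedule in section I.1 lists these tests under Follow-up, at the surgeon's visit 1-4 weeks after the operation: "Blood tests which include a comprehensive metabolic panel (includes liver function and chemistry panel), protime and complete blood count will be drawn". It lists them nowhere else.

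Section I.7 also describes other blood work:
- Optional research blood: "additional research blood samples will be obtained immediately before and 1-4 week following liver resection surgery". Its purpose is "to provide data on germline DNA, RNA, microRNA, and circulating RNA/DNA".
- A fasting lipid profile, linked to Specific Aim 2. It is drawn "If the results of a recent (within 3 months) fasting lipid profile (ie. cholesterol blood test) are not available", and then "at the time other baseline laboratory samples are being obtained by the study". What those other baseline samples contain is not stated.

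On liver status before surgery, section I.2 admits Child-Pugh A and B. Section I.4.1 has test results reviewed to confirm eligibility.

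**The concern.** Liver function after resection depends in part on liver function before it. Because Child-Pugh A and B are both eligible, subjects can enter surgery with different liver function. If PET uptake follows that existing difference, PET will correlate with the post-operative tests even if it tells the surgeon nothing beyond the pre-operative blood results.

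At stake is how an Aim 3 result can be read. With the pre-operative value of the same test to hand, the study can say whether PET carries further information. With only the post-operative value, it can report an association and must leave its source open. The choice of model can wait for the SAP, but which values are collected, and with what dates, is fixed by the protocol.

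**Working it through.** The protocol states no sample size, effect size or correlation for Aim 3, so there is no figure to reproduce. The check is a reading of every place where a pre-operative CMP, protime or blood count could be specified.

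| Place | What it provides | Does it specify the three tests before surgery? |
|---|---|---|
| I.1 Enrollment | Pregnancy test where appropriate | No |
| I.1 Follow-up | The three tests at 1-4 weeks | Post-operative only |
| I.2 | Child-Pugh A/B; alpha-fetoprotein as part of one diagnostic route | No; Child-Pugh is a two-level measure here |
| I.4.1 | Test results reviewed for eligibility; a data list that serves authentication of progression | Not named, not excluded |
| I.6 | Source documents abstracted to list disease sites | Not named, not excluded |
| I.7 research blood | Optional paired samples for nucleic-acid data | No |
| I.7 lipid profile | Serves Aim 2 | No |
| I.7 other baseline samples | Contents undefined | Cannot be told |

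So no visible text specifies a pre-operative value for any of the three tests, and one undefined item may include them.

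**Illustration of the mechanism. All correlations here are assumed; none comes from the protocol.** Let B be the pre-operative value of a test. If PET adds nothing once B is known, then

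crude r(PET, post) = r(PET, B) × r(B, post).

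- r(PET, B) = 0.3 and r(B, post) = 0.5: 0.3 × 0.5 = 0.15.
- 0.5 and 0.7: 0.5 × 0.7 = 0.35.
- 0.7 and 0.8: 0.7 × 0.8 = 0.56.

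Over this range, PET with no added information would still show a crude correlation of 0.15 to 0.56.

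Conversely, suppose that the observed crude correlation is 0.40. The partial correlation given B is

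(0.40 − r(PET, B) × r(B, post)) / √[(1 − r(PET, B)²)(1 − r(B, post)²)].

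- 0.3 and 0.5: (0.40 − 0.15) / √(0.91 × 0.75) = 0.25 / 0.826 = 0.30.
- 0.5 and 0.7: (0.40 − 0.35) / √(0.75 × 0.51) = 0.05 / 0.618 = 0.08.
- 0.7 and 0.8: (0.40 − 0.56) / √(0.51 × 0.36) = −0.16 / 0.428 = −0.37.

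The same crude result is thus compatible with a moderate, a negligible or a reversed adjusted relation. The illustration shows why B is worth recording. It does not estimate the confounding in this study.

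**Timing of the post-operative draw.** The window of 1-4 weeks spans 4 − 1 = 3 weeks. Section I.1 has the blood drawn at the visit, and section I.7 has it after the visit. The date of the draw is therefore worth recording next to the result.

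**The case against.** The strongest reply is that nothing here is wrong. The protocol claims only that PET may be predictive, a crude association is a legitimate result, and baseline adjustment is commonly left to the SAP, which is not shown. The wording of Specific Aim 3 is not in the public copy either, so it cannot be judged whether the aim is association or added value. This stands, and it is why the point is an improvement and not an error.

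Silence in the schedule is also weak evidence. Section I.1 leaves out the lipid profile and the research blood drawn before surgery, both of which section I.7 provides for. The study does obtain some baseline laboratory samples, so the gap may be one of labelling only. This stands too, and the fix allows for it.

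A reader might infer something stronger: that no pre-operative liver information will exist, so that no later analysis could separate PET from prior liver function. The documents do not support this. Child-Pugh class is an eligibility item and permits coarse stratification. Pre-operative results may be in the chart, and section I.6 already has source documents obtained from the medical record after consent. The undefined baseline samples may hold the panel.

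What the reply does not remove is that no visible text ensures uniform, dated capture of the same tests before surgery. Child-Pugh class is also a poor substitute for the test's own pre-operative value.

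**Conclusion.** The point holds as a concrete, low-cost improvement. As written, the Aim 3 comparison yields a crude association that may partly reflect liver function before surgery, and the visible protocol does not state that the matching pre-operative tests are recorded. There is no internal contradiction.

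The size of any confounding cannot be derived from the document. The correlations used above are assumptions that show only the direction of the problem. The conclusion rests on three things: that subjects can differ in liver function before surgery, which eligibility of both Child-Pugh classes allows; that the undefined baseline samples are not already specified elsewhere as including the three tests; and that the unseen wording of Aim 3 does not already settle the matter. Confidence is therefore moderate.

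**What to change.** 1. In sections I.1 and I.7, name CMP, protime and complete blood count among the baseline samples if the study already draws them. If it does not, require the last result of each before surgery to be abstracted from the chart with its date.
2. Record the date of the post-operative draw.
3. State in section I.7 that the Aim 3 comparison accounts for the same test's pre-operative value, and that the unadjusted result is reported as a crude association.

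Model form, main measure and further covariates can stay with the SAP.

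The cost is a little chart abstraction, date fields, and two or three sentences of text. No new visit or blood draw is needed. Subjects with no pre-operative value drop out of the adjusted comparison but remain in the crude one, so the number in each should be reported.
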